Patients will be followed both clinically and radiographically (CT) at baseline then every 8 weeks after starting the treatment. Responses will be assessed using RECIST 1.1 criteria. Dose level 1 (4000 µg) will be the starting dose in the standard 3+3 dose escalation design. Three patients will be recruited for Dose level 1.

The next three patients will be recruited for Dose level -1 (2500 µg). While none of the three patients in Dose level 1 experienced a DLT, there were significant side effects. If 0 of three patients at Dose level -1 experiences a DLT related to SLM, then dose escalation will proceed to the next dose level (3000 µg).

If one of the three patients at Dose level -1 experiences a DLT related to SLM, then three more patients will be treated at the same dose. If exactly one out of six patients experiences a DLT, then dose escalation will proceed to the next dose level (3000 µg) after discussion at the weekly SLM meeting.

If two of the first three patients experience DLT related to SLM, then the dose will de-escalate to the lower dose (1500 µg).

The next patient can be enrolled after the previous patient's 28th Day of SLM assessment, provided there are no DLTs related to SLM. The minimum number of patients required is 6 and the maximum is 12.

Dose Limiting Toxicities:

DLTs related to SLM will be defined as any of the following events determined by the Investigator to be related to treatment combination irrespective of outcome. This applies to the first cycle only (2 weeks SLM alone + 4 weeks combination therapy):

- Clinically significant non-hematologic toxicity of Grade 3 or greater not related to underlying malignancy.
- Severe hematological toxicity (Grade 4 neutropenia, Grade 3-4 febrile neutropenia, or Grade 4 thrombocytopenia).
- If resolution of DLT related to SLM does not occur in 4 weeks, then patient will be withdrawn from the study.
- Grade 4 nausea, vomiting, diarrhea, or electrolyte imbalances or Grade 3 nausea, vomiting, diarrhea and electrolyte imbalances lasting greater than 48 hours despite optimal medical intervention.
- In the dose escalation phase, treatment delays related to the study drug that last >2 weeks

- Any grade 3 or higher DLT related to SLM alone will be discussed at the weekly SLM committee meeting.
-

Expansion Part 2: Enrollment Completed

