5.5 DURATION OF FOLLOW-UP

Patients will be followed up, until they are lost to follow-up or death, whichever occurs first. Patients removed from study for unacceptable adverse event(s) will be followed for resolution or stabilization of the adverse event as well. Follow up off study will be performed using telephone contact correspondence with treating physicians, and death records as necessary to update vital status at least every 6 months.

5.6 EVALUATIONS DURING SCREENING AND TREATMENT:

The following evaluations and assessments will be performed at the specified times listed in the study calendar (section 11.0):

- Physical examination
- Vital signs including blood pressure with each visit
- Assessment of ECOG performance status
- Clinical Chemistries
- CBC with differential
- Urinalysis
- Glucose
- Erythropoietin levels
- Lipid Panel
- Coagulation levels
- Blood sample(s) for SLM concentration analysis, miRNA samples and additional blood for storage.
- Pregnancy test for women of childbearing potential.
- EKG
- Dual Energy CT Scans will occur at Screening, Day 14 and Cycle 3(8 weeks after first dose of SLM plus Axitinib)
- Disease assessments CT +/- Bone Scan will begin at Cycle 5 Day 1(every 8 weeks +/- 5 days). These scans will be performed as determined by the treating physician. If subject is asymptomatic, bone scans may be done every 4 months.
- Concomitant medications
- All treatment-related adverse events should be followed until resolution or stabilization.
- Safety phone call to assess subject status. Archival tumor tissue collection, if availableFresh Tumor Tissue Biopsy at Screening, Day 14 and Cycle 3 (+/- 3 days both occasions) and preferable at progression, for up to 20 patients in Expansion Phase and the Pilot phase, if accessible and deemed safe by physician.

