11.0 STUDY CALENDAR - SLM + AXITINIB FOR CLEAR CELL RCC

Evaluation	Screening Day ² -28 prior to Day 0				SLM Run-in Phase (+/- 2 days)				Cycle 1 (+/- 3 days)				Cycle 2 and subsequent cycles (+/- 3 days) ¹⁶				End of Treatment (28 days +/- 7 days) after last dose	Follow-up occurring approximately every 6 months
	Week 1	Week 2	Week 1	Week 2	Week 3	Week 4	Week 1	Week 2	Week 3	Week 4	Week 2	Week 3 ⁶	Week 4	Week 2	Week 3 ⁶	Week 4		
Informed consent	X																	
Verify eligibility criteria	X																	
Medical History ¹	X				X													
Concurrent medication	X				X													
Vital signs	X				X													X
Physical exam ¹	X				X													X
Performance status evaluation	X				X													X
ECG	X																	
Lipid Panel	X																	
CBC w/diff	X				X													X
ALT, AST, Alk phos, T.bili Na, K, calcium, magnesium, BUN, creatinine, T. protein, albumin, LDH	X				X													X
Erythropoietin, serum	X																	
Urinalysis	X				X	Day 14												X
Pregnancy test for WOCCBP	X				X													X
PT/INR, PTT	X																	
Glucose	X																	X
miRNA (blood draw) ⁸			Day 1	Day 14														
Fresh Tumor Tissue biopsy			Day 1	Day 14														
IHC (up to 20 patients in expansion phase and pilot phase) ¹³																		
SLM Concentration ⁸			X ⁸	X ⁸														
Archival tumor tissue			X ⁸	X ⁸														
Additional blood for storage ⁸			X ⁸	X ⁸														

CT +/- Bone scan ³				Beginning at Cycle 5 Day 1 Imaging will be repeated every 8 weeks +/- 5 days. ^{14,17}
CT +/- Bone scan ³	X ⁷			Scans will be repeated every 8 weeks +/- 5 days, starting 8 weeks after first dose of SLM plus Axitinib, as clinically indicated. ¹⁷
Escalation Phase				
Dual Energy CT ¹⁵	X ⁷	Day 14		8 weeks after first dose of SLM plus Axitinib (Cycle 3)
Expansion/Pilot Phase				
SLM Dosing				
Axitinib Dosing				
Adverse Event Assessment				
Safety Phone Call		X	X	X ¹¹

¹ History and physical exam will be performed by physician and/or midlevel provider or designated fellow. To include cardiac risk factors, smoking history, family history of cardiac disease, use of aspirin.

² Events may be performed Day 1 of SLM run-in if resulted/reviewed prior to dosing.

³ CT scan (with or without Contrast) of chest, abdomen and pelvis with or without bone scan based on provider's judgment. Bone Scans will only be repeated if lesion is present at baseline.

⁵ These labs will be drawn as clinically indicated.

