⁶ Visit 3 for Cycle 2 and beyond will only occur if clinically indicated.

⁷ Screening CT to be performed within 28 days from SLM Day 1.

⁸ See Table 20.0 for Escalation patients. See Table 20.1 for Expansion patients. See Table 20.2 for Pilot Phase patients.

⁹ Cycle 3 only

¹⁰ Blood drawn for glucose testing every even cycle beginning with Cycle 2.

¹¹ Patients will be followed up, until they are lost to follow-up or death, whichever occurs first. Patients removed from study for unacceptable adverse event(s) will be followed for resolution or stabilization of the adverse event as well. Follow up off study will be performed using telephone contact, correspondence with treating physicians, and death records as necessary to update vital status at least every 6 months.

¹² Archival tumor tissue will be obtained, if available and if subject agrees.

¹³ Fresh research tissue biopsies will occur in up to 20 subjects enrolled into the Expansion Phase and pilot phase, that the PI deems as safe and tumor is accessible. An additional fresh research tissue biopsy may occur at progression for subjects that the PI deems as safe and tumor is accessible.

¹⁴ CT +/- Bone scans will be performed as clinically indicated beginning at Cycle 5, Day 1. Prior to Cycle 5, Day 1 Dual Energy CT's will be performed.

¹⁵ For subjects in expansion phase and pilot only Dual Energy CT's will follow protocol as outlined in Section 22.

¹⁶ Per PI or Sub-J discretion, subjects may be seen at odd cycles after Cycle 11 is completed (Cycle 11, 13, 15, 17, etc). Subjects who are allowed to be seen at odd cycles will be dispensed with 8 weeks of study drug and asked to contact the research team with any issues or concerns between visits. (if patient is seen at odd cycles then no assessments are required at even cycles. Labs may be obtained locally.)
¹⁷ If subject is asymptomatic, bone scans may be done every 4 months.

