12.2 RESPONSE CRITERIA

For the purposes of this study, patients should be re-evaluated for response every 8 weeks (every other cycle) by CT scans for body images.

12.2.1 Response and progression will be evaluated in this study using the new international criteria proposed by the revised Response Evaluation Criteria in Solid Tumors (RECIST) guideline (version 1.1) [Eur J Ca 45:228-247, 2009]. Changes in the largest diameter (unidimensional measurement) of the tumor lesions and the shortest diameter in the case of malignant lymph nodes are used in the criteria.

- Evaluable for toxicity: All patients will be evaluable for toxicity from the time of their first treatment with SLM. Toxicities will be measured using the CTCAE criteria, version 4.03
- Evaluable for objective response: Only those patients who have measurable disease present at baseline, have received at least one cycle of therapy, and have had their disease re-evaluated will be considered evaluable for response. These patients will have their response classified according to the definitions stated below. (Note: Patients who exhibit objective disease progression prior to the end of cycle 1 will also be considered evaluable.)
- Evaluable Non-Target Disease Response: Patients who have lesions present at baseline that are evaluable but do not meet the definitions of measurable disease, have received at least one cycle of therapy, and have had their disease re-evaluated will be considered evaluable for non-target disease. The response assessment is based on the presence, absence, or unequivocal progression of the lesions.

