12.3.1.5 Progression-Free Survival

- PFS is defined as the duration of time from start of treatment to time of progression or death, whichever occurs first.

Table 4: For Patients with Measurable Disease (i.e., Target Disease)

Target Lesions	Non-Target Lesions	New Lesions	Overall Response	Best Overall Response when Confirmation is Required*
CR	CR	No	CR	≥ 4 wks. Confirmation**
CR	Non-CR/Non-PD	No	PR	≥ 4 wks. Confirmation**
CR	Not evaluated	No	PR	
PR	Non-CR/Non-PD/not evaluated	No	PR	
SD	Non-CR/Non-PD/not evaluated	No	SD	Documented at least once ≥ 4 wks. from baseline**
PD	Any	Yes or No	PD	no prior SD, PR or CR
Any	PD***	Yes or No	PD	
Any	Any	Yes	PD	

* See RECIST 1.1 manuscript for further details on what is evidence of a new lesion.
 ** Only for non-randomized trials with response as primary endpoint.
 *** In exceptional circumstances, unequivocal progression in non-target lesions may be accepted as disease progression.
Note: Patients with a global deterioration of health status requiring discontinuation of treatment without objective evidence of disease progression at that time should be reported as "*symptomatic deterioration*." Every effort should be made to document the objective progression even after discontinuation of treatment.

For Patients with Non-Measurable Disease (i.e., Non-Target Disease)

Non-Target Lesions	New Lesions	Overall Response
CR	No	CR
Non-CR/non-PD	No	Non-CR/non-PD*

Not all evaluated	No	not evaluated
Unequivocal PD	Yes or No	PD
Any	Yes	PD
* ‘Non-CR/non-PD’ is preferred over ‘stable disease’ for non-target disease since SD is increasingly used as an endpoint for assessment of efficacy in some trials so to assign this category when no lesions can be measured is not advised		

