12.3.1.6 Response Review

Patients with measurable disease will be assessed by standard criteria. The purpose of tumor measurements will be to assess benefit to the patients from treatment and to determine appropriateness for continuing on study. For the purposes of this study, patients should be re-evaluated every week to every six weeks according to the study guidelines and undergo imaging studies as highlighted in the study calendar. Following documentation of an objective response, confirmatory scans will also be obtained a minimum of eight weeks later.

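### CT from Cycle 5 is fixed at every 8 weeks in some places and left to clinical discretion in others, which can lengthen the single-arm PFS estimate

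*Combined protocol and SAP*

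**What the plan says.** **Fixed interval.** The expansion/pilot row of the study calendar (section 11.0) reads "Beginning at Cycle 5 Day 1 Imaging will be repeated every 8 weeks +/- 5 days". Section 12.2 says "patients should be re-evaluated for response every 8 weeks (every other cycle) by CT scans for body images". Section 5.1, in its text on Escalation Part 1, says "Patients will be followed both clinically and radiographically (CT) at baseline then every 8 weeks after starting the treatment".

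**Discretion.** Footnote 14, attached to that same expansion/pilot row, reads "CT +/- Bone scans will be performed as clinically indicated beginning at Cycle 5, Day 1". Section 5.6 gives the 8-week interval and its window for CT with or without bone scan, then adds "These scans will be performed as determined by the treating physician". The escalation row of the calendar carries similar words, "Scans will be repeated every 8 weeks +/- 5 days, starting 8 weeks after first dose of SLM plus Axitinib, as clinically indicated", but that part is complete.

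**A further interval.** Section 12.3.1.6 says "patients should be re-evaluated every week to every six weeks according to the study guidelines", with imaging according to the calendar.

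**The endpoint.** Section 12.3.1.5 states: "PFS is defined as the duration of time from start of treatment to time of progression or death, whichever occurs first". Section 12.1 has progression documented by the individual investigator. Section 14.4 singles out PFS as the main interest of Part 2 and sets a null median of 8 months against 14 months. It assumes exponential times, a Wald test at 10% (one-sided), 19 patients, 18 months of accrual and 14 months of follow-up. Section 14.9 names ITT and according-to-protocol analyses but has no rule for late or missed scans.

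**The concern.** Progression is dated by the scan that shows it. If a patient who feels well can miss a scheduled CT without a deviation, progression is found later and recorded PFS is longer. In a randomized trial a shared schedule would largely cancel such a delay. Here there is no concurrent arm (section 14.5), the benchmark is a fixed historical figure, and the people who assess progression also decide on the scan. The error from skipped scans runs towards the hoped-for result. The estimate is meant to shape a larger trial, so the scan schedule behind it should be known.

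**Working it through.** **When discretion starts.** The run-in is 14 days and cycles are 28 days. Counting from SLM Day 1, Cycle 3 Day 1 is week 2 + 8 = 10 and Cycle 5 Day 1 is week 2 + 16 = 18. CTs before Cycle 5 (baseline, Day 14, Cycle 3) are fixed dual-energy scans. With an exponential median of 8 months, λ0 = ln 2/8 = 0.0866 per month. Week 10 is 10 × 7/30.4375 = 2.30 months, and exp(−0.0866 × 2.30) = 0.82. About 82% of events would thus fall after the last fixed scan.

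**The plan's own figure.** With uniform accrual over 18 months and 14 months beyond it, expected events are d = 19 × [1 − (e^(−14λ) − e^(−32λ))/(18λ)]. This gives 16.1 at a median of 8 months and 12.7 at 14 months. On the median scale:
- critical value: 8 + 1.2816 × 8/√16.1 = 10.55;
- power: Φ[(14 − 10.55)/(14/√12.7)] = Φ(0.88) = 0.81.

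The stated 80% is reproduced. A log-scale Wald test gives 0.76 by formula and 0.78 by simulation.

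**Effect of slipped scans.** Simulation used 100,000 trials of 19 patients, with the accrual and follow-up above. Each progression is dated at the next scan: week 10, then every 8, 12 or 16 weeks. The rate estimate is λ̂ = d/(total observed time). The log-scale test rejects when ln(λ0/λ̂) × √d > 1.2816, and the rate-scale test when (λ0 − λ̂)/(λ̂/√d) > 1.2816. The plan does not say which scale it uses.

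The documents do not say on what scan schedule the 8-month benchmark was read. Assume it was read on 8-weekly scans. The underlying scan-free median that then yields an observed 8.0 months is 7.29 months.

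| Spacing after week 10 (assumed) | Estimated median, months | False positive, log scale | False positive, rate scale |
|---|---|---|---|
| 8 weeks | 8.00 | 7.5% | 10.9% |
| 12 weeks | 8.28 | 10.1% | 14.2% |
| 16 weeks | 8.56 | 13.3% | 18.3% |

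The shift is 0.28 to 0.56 months. The larger value is 0.56/6 = 9% of the 6-month target difference. If the week-18 scan is kept and only later scans are spaced out, the log-scale rates are 7.4%, 9.9% and 12.5%, and 19.8% at 24 weeks.

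**Random skipping from Cycle 5, with and without symptom-triggered scans.** The benchmark assumption is the same. The skip rates and the share of progressions scanned at once because of symptoms are also assumptions.

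| Skipped | Symptom-triggered | Median, months | Log scale | Rate scale |
|---|---|---|---|---|
| 0% | 0% | 8.0 | 7.6% | 11.0% |
| 0% | 30% | 7.8 | 6.2% | 9.0% |
| 25% | 0% | 8.3 | 10.8% | 15.2% |
| 25% | 30% | 8.0 | 8.1% | 11.7% |
| 50% | 0% | 9.0 | 20.8% | 27.1% |
| 50% | 30% | 8.5 | 13.6% | 18.5% |

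**Kaplan-Meier median.** Section 14.3.2 reports this. It falls on scan dates and so moves in steps: week 34 is 7.8 months and week 42 is 9.7 months. In the simulation, 25% skipping without symptom-triggered scans moved it from the first to the second.

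**The case against.** The strongest reply is that the fixed schedule is the better reading. Footnote 14 goes on to say that dual-energy CT is used before Cycle 5, so its purpose may be only to mark the change to ordinary CT. Footnote 3 ties provider judgment to the bone scan, and the only stated relaxation, to every 4 months, is for bone scans. Section 7.1 speaks of the next scheduled assessment and dates confirmed progression back to first suspicion. The odd-cycle visits allowed by footnote 16 keep an 8-week rhythm. No passage states a CT interval longer than 8 weeks.

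Much of this stands: slippage is permitted, not planned. It does not remove the conflict, because footnote 14 names CT and bone scans already have their own rules. The sentence in section 5.6 is less clear and could refer to the bone scan alone.

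Three stronger readings are tempting, and the documents do not support them.
- *The wording inflates PFS.* Discretion can also bring scans forward, and deaths are events whose dates do not depend on scans. With 25% of scans skipped and 30% of progressions scanned on symptoms, the estimate returns to 8.0 months.
- *The false-positive rate is 15% to 32%.* Treating 8 months as a scan-free median gives about 15%, 18%, 22% and 32% at 8, 12, 16 and 24 weeks. The 15% arises under the 8-week schedule itself, so the wording does not cause it, and no document figure supports the wider spacings. If 20% of events did not depend on scans (assumption), the series would be 13%, 16%, 19% and 26%.
- *Three passages loosen the schedule for the PFS cohort.* One of them is the row for the completed escalation part.

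It is also true that PFS is a secondary objective, that section 14.4 calls its null hypothesis imperfect and its purpose hypothesis generating, and that no go/no-go rule depends on the test.

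**Conclusion.** The inconsistency is real and reaches the expansion and pilot cohorts. A skipped CT in a well patient could be defended as compliant, and no analysis rule limits the effect. This can lengthen PFS but need not.

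Under 12- to 16-week spacing, and with a benchmark read on 8-weekly scans, the gain is about 0.3 to 0.6 months. The log-scale false-positive rate rises from about 7.5% to about 10–13% (rate scale: about 11% to 14–18%). That is small beside the 6-month target difference but noticeable for a one-sided 10% test. The size rests on assumed spacings and an assumed benchmark schedule, and on dating every event at a scan. Heavy skipping would make it larger; deaths and symptom-triggered scans make it smaller or cancel it. The point merits correction but does not undermine the trial's primary safety and dose objectives.

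**What to change.** 1. Reconcile section 5.1, section 5.6, the calendar rows with footnote 14, section 12.2 and section 12.3.1.6 to one tumor-imaging schedule: the 8 weeks ± 5 days already written. Limit discretion to bone scans and to extra, unscheduled scans. Part 2 enrollment is complete, so this can affect only patients still being scanned.
2. For scans already done, report the actual intervals between CTs by cohort.
3. Add a PFS sensitivity analysis with progression interval-censored between the last negative and the first positive scan, and deaths at their own dates. Read it beside the main estimate, not as a second test against 8 months. Even with perfect 8-week scanning it would sit lower (7.3 against 8.0 months under the assumption above).

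The cost is a wording change and one extra analysis. No scans are needed beyond the schedule already in the protocol, and PFS remains a secondary, hypothesis-generating estimate.

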4.1.1 Consent Process

Subjects will be consented by a member of the study team after receiving an explanation of the study, review of the consent form, and having had all questions answered by a member of the study team. . The subject will be provided with a copy of the signed consent form.

An automatic notification will be sent to appropriate staff, including the safety officer after consent, following entry of patient information into the clinical trials management system (OnCore).

4.1.2 Eligibility Assessment:

Eligibility will be assessed according to the protocol. An eligibility check list will be completed and signed by the treating physician, documenting his/her review of all eligibility criteria and confirming all screening assessments have been completed and the subject meets criteria to begin protocol treatment. Once eligibility is confirmed by the treating physician, a signed copy of the eligibility checklist will be scanned and entered into OnCore and automatic notifications sent to appropriate staff.

Disease assessment is to be performed within the 28 days prior to the start of study treatment using CT scan of chest, abdomen and pelvis with or without bone scan based on provider's judgment. Patient disease assessment will be performed according to RECIST 1.1 criteria for solid tumors.

The following pre-treatment evaluations are to be performed within 28 days prior to the start of treatment:

- Compliance with eligibility criteria
- Patient demography
- Medical history (to include a complete history of previous, present and concomitant conditions and treatment)
- Physical examination (complete physical examination, including height, weight and BSA)
- Vital signs (to include blood pressure, heart rate, respiratory rate, and body temperature)
- Assessment of ECOG performance status
- CBC with differential to include: hemoglobin, differential white blood cell count, platelet count. Coagulation parameters including INR (International Normalized Ratio), aPTT, and PT.

- Clinical chemistries to include: ALT, AST, total bilirubin, sodium, potassium, calcium, magnesium, urea, creatinine (creatinine clearance calculated using the Cockcroft and Gault formula), total protein, albumin, LDH, Alkaline phosphate.
- Urinalysis
- Glucose
- Erythropoietin per calendar
- Assessment of cardiac risk factors (Lipid profile, smoking, family history of cardiac disease, use of aspirin)
- Concomitant medications
- 12-Lead ECG after 5 minutes supine rest.

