- A urinalysis for protein will be performed before starting axitinib and monthly while on it, and if more than 2+ is detected, urine protein to creatinine (UPC) ratio is to be determined (or 24 hour urine protein excretion).
- Blood pressure will be measured with every office visit, patient will be asked to keep a diary with daily record of blood pressure at home. Development of a hypertensive crisis will mandate discontinuation of the drug.
- Hematology and biochemistry will be assessed each clinic visit.
- Physical examination and vital signs will be assessed at baseline and with each clinic visit.

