7.0 DOSING DELAYS/ DOSE MODIFICATIONS

Adverse Event	Action with Axitinib	Action with SLM
DLT during Run-in (see section 14.4)	NA	Permanently D/C Treatment
Grade 4 Hematologic (not controlled by standard supportive care)	Hold drug until resolved to grade 1*; restart at same dose level; if same grade 3 event re-occurs then hold until resolved to grade 1* and reduce drug as noted below**	Hold drug until resolved to grade 1*. No dose reductions.
Grade 3-4 Non-hematologic (not controlled by standard supportive care)	Hold drug until resolved to grade 1*; restart at same dose level; if same grade 3 event re-occurs then hold until resolved to grade 1* and reduce drug as noted below**	Hold drug until resolved to grade 1*. No dose reductions.
Grade 2 weight loss	Continue drug but consider dose reduction**	Continue treatment
Proteinuria > 2+ with urine protein creatinine (UPC) ratio 2.0 or greater, or 24 hour urine protein is >2 grams	Hold and repeat urine creatinine protein ratio or 24hr urine in 1 week. Resume treatment when ratio < 2.0 or under 2g/24hr; If protein >3.5g/24, hold drug and repeat 24 hr urine and creatinine clearance weekly. May resume when under 2g/24hr. Consider dose reduction if event re-occurs.	Continue treatment
Hypertension >150 systolic or >90 diastolic which is recurrent or persistent after maximum antihypertensive treatment	Interrupt until <150 systolic and <90 diastolic and reduce dose as noted below**	Continue treatment

*If patient's baseline value is > grade 1, then interruptions should resolve to baseline value or grade 1 whichever is appropriate for the patient.

**If dose reduction from 5mg twice daily is required, the recommended dose is 3mg twice daily. If additional reduction is required, the recommended dose is 2mg twice daily.

7.1 GENERAL GUIDELINES:

Patients who cannot resume treatment within 6 weeks due to persistent toxicities should be withdrawn from the study.

Axitinib dose can be re-escalated after symptoms improve to grade 1 and per provider discretion.

Over the course of treatment, management of some adverse drug reactions may require temporary interruption up to one week of one or both drugs per the provider discretion and after discussion with patient even if the symptoms are not grade 3/4. From previous experience in the dose escalation phase, both patients and provider found these periodic interruptions to be helpful for the patient quality of life.

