Plasma concentrations of axitinib may be altered by the concomitant use of drugs that affect the cytochrome P450 isoenzymes CYP3A4 and CYP3A5. Strong inhibitors of these enzymes should be avoided, but if they must be used then the dose of axitinib should be reduced. Grapefruit and grapefruit juice should also be avoided. Moderate and strong inducers of these enzymes can reduce axitinib concentrations and should therefore be avoided during axitinib therapy.

Toxicities of axitinib

- The most common adverse effects of axitinib include gastrointestinal disturbances, reduced appetite, weight loss, fatigue, asthenia, dysphonia, and palmar-plantar erythrodysesthesia.
- Hypertension is also common and cases of hypertensive crisis have been reported. Blood pressure should be well-controlled before starting axitinib and monitored during therapy. Antihypertensive treatment may be needed but the dose of axitinib should be reduced if hypertension persists; axitinib should be stopped if hypertension is severe and persistent or there is evidence of hypertensive crisis. Arterial and venous thromboembolism have occurred in patients given axitinib. Reported hemorrhagic events have included cerebral hemorrhage, hematuria, and gastrointestinal bleeding. Gastrointestinal perforation and fistula formation have also been reported.
- Other adverse effects include thyroid dysfunction, proteinuria, and elevations of liver enzymes values; patients should be assessed for these before starting axitinib and monitored during therapy. There have also been cases of reversible posterior leukoencephalopathy syndrome in patients given axitinib.
- Axitinib should be stopped at least 24 hours before surgery, because of potential impairment of wound healing. (Last reviewed: 2012-03-05; last modified: 2012-03-26)

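### Odd-cycle visits after Cycle 11 conflict with the monthly urine-protein check and leave no required on-treatment glucose after Cycle 10

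*Combined protocol and SAP*

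**What the plan says.** Four parts of the protocol bear on this.

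- **Study Calendar (section 11.0), footnote 16.** At the discretion of the PI or a sub-investigator, "subjects may be seen at odd cycles after Cycle 11 is completed". These patients receive 8 weeks of study drug at a time. The footnote continues: "if patient is seen at odd cycles then no assessments are required at even cycles. Labs may be obtained locally".
- **Section 6.0, Safety Assessments.** "A urinalysis for protein will be performed before starting axitinib and monthly while on it". Nothing limits this to early cycles. The same section says: "Hematology and biochemistry will be assessed each clinic visit".
- **Study Calendar, footnote 10.** "Blood drawn for glucose testing every even cycle beginning with Cycle 2".
- **Section 5.7, End of treatment.** Glucose and urinalysis are both done 28 days (+/- 7) after treatment stops.

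Two further sections show what the urine test is for. Section 9.0 lists proteinuria among the axitinib effects for which "patients should be assessed for these before starting axitinib and monitored during therapy". The dose-modification table in section 7.0 requires an axitinib hold for "Proteinuria > 2+ with urine protein creatinine (UPC) ratio 2.0 or greater", or for more than 2 g of protein in a 24-hour urine.

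**The concern.** Two safety tests stop lining up with the visits once a patient is on the footnote 16 schedule.

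For urine protein, section 6.0 requires a monthly test while footnote 16 says nothing is required at every second cycle. Footnote 16 does not say that it overrides section 6.0. Staff working from the calendar alone would therefore breach section 6.0. The patient, holding 8 weeks of axitinib, could go twice as long before the measurement that triggers a hold. Proteinuria is found by testing, so asking patients to call the team if something is wrong does not replace the test.

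For glucose, the even-cycle index in footnote 10 was not adjusted for patients who attend only odd cycles. The test stays on the schedule but has no required visit left at which to be done.

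**Working it through.** The plan gives no figure to reproduce, so the check lists the required tests cycle by cycle.

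**Inputs**
- Cycle length: 28 days after the SLM run-in (section 5.2).
- Visit window from Cycle 2 onward: +/- 3 days (section 11.0).
- Urine protein: monthly on axitinib, taken here as once per 28-day cycle (section 6.0).
- Glucose: Cycles 2, 4, 6 and so on (footnote 10).
- Footnote 16: required visits at Cycles 11, 13, 15 and so on, so Cycle 12 is the first one skipped.
- Illustrative patient (an assumption): moved after Cycle 11 and treated through Cycle 24, that is 13 cycles or 13 x 4 = 52 weeks.

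**Counts over Cycles 12 to 24**
- Odd cycles: 13, 15, 17, 19, 21, 23 = 6.
- Even cycles: 12, 14, 16, 18, 20, 22, 24 = 7.

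| Test | Required without footnote 16 | Required with footnote 16 |
|---|---|---|
| Urine protein | 13 (section 6.0) | 6 (section 6.0 less the even cycles) |
| On-treatment glucose | 7 (footnote 10) | 0 |

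Ending at Cycle 25 instead gives 14 urine checks against 7, so the ratio of about two to one does not depend on the stopping point.

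**Urine-protein interval**
- Nominal: 28 days against 2 x 28 = 56 days.
- Longest gap the windows allow: 28 + 6 = 34 days against 56 + 6 = 62 days.
- Mean wait from onset to the next required test, if onset is uniform within the interval (interval / 2): 14 days against 28 days.

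**Timing of the glucose gap**
- Last required on-treatment draw, Cycle 10 Day 1: 9 x 28 = 252 days = 36 weeks after axitinib starts.
- First waived draw, Cycle 12 Day 1: 11 x 28 = 308 days = 44 weeks.
- Next required draw: the end-of-treatment visit, about 28 days after the last dose.

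**Does biochemistry at each visit cover glucose?** It does not appear to. Section 4.1.2 defines the panel: "Clinical chemistries to include: ALT, AST, total bilirubin, sodium, potassium, calcium, magnesium, urea, creatinine", followed by total protein, albumin, LDH and alkaline phosphatase. Glucose is a separate item there, and is again listed apart from the chemistries in sections 5.6 and 5.7 and in the calendar.

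**Does imaging have the same problem?** It does not. CT starts at Cycle 5 Day 1 and repeats every 8 weeks (Cycles 5, 7, 9, 11, 13 and so on), so it falls on odd cycles.

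**The case against.** The strongest reply is that both texts can be obeyed. Footnote 16 does not cancel section 6.0, and its remark about local laboratories may be meant as the route for tests that fall due between visits. On that reading this is an ambiguity, and a breach occurs only if staff overlook section 6.0. It is true that a local monthly test would satisfy both texts. But the remark is permissive, names no test or interval, and follows a statement that nothing is required. It allows the test without keeping it mandatory.

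A second reply is that the calendar cells for urinalysis and glucose from Cycle 2 onward cannot be read in the available text, and that footnote 5, on drawing labs as clinically indicated, cannot be tied to a row. That is a real limit. The counts above do not use those cells, however. They follow from section 6.0 and footnotes 10 and 16.

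A third reply is that the stakes are small, and much of this stands. The move is discretionary and comes only after 11 cycles, so a patient with known proteinuria can be kept on monthly visits. Patients are asked to contact the team between visits and keep a daily home blood-pressure record. Providers may interrupt either drug at lower grades. No listed toxicity or dose rule involves glucose. An 8-weekly urine check in stable long-term patients may even be intended, but section 6.0 would then need to say so. None of these safeguards supplies the urine measurement that section 7.0 depends on.

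**Conclusion.** The concern holds. For patients moved to odd-cycle visits, footnote 16 as written conflicts with the monthly urine-protein rule, doubling the required interval from 28 to 56 days. It also leaves no required on-treatment glucose after Cycle 10. Through Cycle 24 this means 6 urine checks against about 13, and 0 glucose draws against 7.

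These figures treat monthly as every 28 days and count only required tests. A test ordered on clinical grounds or done locally would shorten the gaps. The 14-day and 28-day mean waits also assume uniform onset.

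The weight is low. Patients who stay on monthly visits are unaffected, end-of-treatment glucose and urinalysis remain, and the number of patients moved is not given. No error rate, power or efficacy estimate changes. This is a minor correction to the safety schedule, and the urine-protein part is the more important of the two.

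**What to change.** 1. **Footnote 16:** state that the even-cycle waiver does not cover urine protein, which is to be obtained locally at each skipped even cycle. The interval returns to 28 days.
2. **Footnote 10:** state that patients under footnote 16 have glucose drawn at the odd cycles they attend (13, 15, 17 and so on). This restores an 8-weekly draw, the frequency footnote 10 already gives.

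The cost is two footnote edits. Glucose is added to a visit that already takes place, and the urine test is at most one local sample per skipped cycle, which section 6.0 already requires.

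If the sponsor does intend 8-weekly urine protein for these patients, section 6.0 could be amended to say so. That would make the texts agree without extra tests, but it accepts the longer interval and should be a stated decision.
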